10.5 CONTINUING REVIEWS AND CLOSEOUT REPORTS

The PI is responsible for submitting the required continuing review reports and associated documents to the WRAIR IRB, KEMRI SERU and Kenya PPB, allowing enough time for review and continuation determination before the established continuing review date. A closeout report will be submitted after ten years or upon completion of the study, whichever occurs first. The WRAIR HSPB will submit continuing review and the closeout reports to the USAMRDC, ORP, HRPO as per SOP UWZ-C-636.

10.6 REGULATORY AUDITS

The knowledge of any pending compliance inspection or visit by the US FDA, OHRP, Kenya PPB, or other government agency concerning clinical investigation or research, the issuance of Inspection Reports, FDA Form 483, warning letters or actions taken by any regulatory agencies including legal or medical actions and any instances of serious or continuing noncompliance with the regulations or requirements will be reported immediately to the sponsor (DAIDS) and WRAIR HSPB and KEMRI SERU. The WRAIR HSPB will report knowledge of any pending inspections/audits by regulatory agencies to the USAMRDC, ORP, HRPO.

11 ESSENTIAL AND SOURCE DOCUMENTS

11.1 SOURCE DOCUMENTS

Source documents are original documents, data, and records from which the participant's data are obtained. These include but are not limited to hospital records, clinical and office charts, laboratory and pharmacy records, diaries, radiographs, and correspondence. The diary card is not a source document but a memory aid for volunteers, as has been done with prior MHRP vaccine trials (e.g. RV306); the information gained from the review of the diary card and the interview with participants will be documented using a combination of progress notes and CRFs maintained in the participants research chart.

11.2 ESSENTIAL DOCUMENTS

The participating site will maintain appropriate medical and research records in compliance with ICH E6 and regulatory and institutional requirements for the protection of confidentiality of subjects. The site will permit authorized representatives of the DAIDS, its designees, and appropriate regulatory agencies to examine (and when required by applicable law, to copy) clinical records for the purposes of quality assurance reviews, audits, and evaluation of the study safety and progress. These representatives will be permitted access to all source data and source documents, which include, but are not limited to, hospital records, clinical and office charts, laboratory notes, memoranda, or evaluation checklists, pharmacy dispensing records, recorded data from automated instruments, copies or transcriptions certified after verification as being accurate and complete, microfiches, photographic negatives, microfilm or magnetic media, x-rays, and subject files and records kept at the pharmacy, at the laboratories, and medico-technical departments involved in the clinical trial.

The investigator and staff are responsible for ensuring maintenance of a comprehensive and centralized filing system of all study-related (essential) documentation, suitable for inspection at any time by representatives of the following: KEMRI SERU, PPB, USAMRDC, ORP, HRPO the NIAID, the FDA, the Kenya Ministry of Health, WRAIR, the people who work for these organizations, and other local, US or international regulatory agencies. Essential documents for all study participants are to be maintained by the investigators in a secure storage facility. Elements include:

- Participant files containing completed informed consent forms, and copies of source documentation
- Study files containing the protocol will include all amendments and copies of correspondence between the study site, protocol team and the IRB
- All Essential Documents outlined in the ICH Good Clinical Practice Guideline.

In addition, all original source documentation must be maintained and be readily available for monitoring or auditing purposes.

12 ADMINISTRATIVE AND LEGAL OBLIGATIONS

12.1 CONDUCT OF THE RESEARCH STUDY

This research study will be conducted per GCP, International Conference on Harmonization (ICH) guidelines, DoD Directive 3216.2, the Declaration of Helsinki, the Belmont Report, the U.S. Code of Federal Regulations 21 CFR 312, 812, 50 and 56, 45 CFR 46 and 32 CFR 219, and all applicable Kenyan laws and regulations.

12.2 PROTOCOL REGISTRATION

12.2.1 INITIAL REGISTRATION

Prior to implementation of this protocol, and any subsequent full version amendments, the site must have the protocol and the protocol informed consent forms approved, as appropriate, by KEMRI SERU and any other applicable regulatory entity (RE). Upon receiving final approval, sites will submit all required protocol registration documents to the DAIDS Protocol Registration Office (DAIDS PRO) at the Regulatory Support Center (RSC). The DAIDS PRO will review the submitted protocol registration packet to ensure that all of the required documents have been received.

The informed consent forms (ICFs) **WILL** be reviewed and approved by the DAIDS PRO and the site will receive an Initial Registration Notification from the DAIDS PRO that indicates successful completion of the protocol registration process. A copy of the Initial Registration Notification should be retained in the regulatory files.

12.2.2 AMENDMENTS

Upon receiving final IRB/EC and any other applicable RE approval(s) for an amendment, sites should implement the amendment immediately. Sites are required to submit an amendment registration packet to the DAIDS PRO at the RSC. The DAIDS PRO will review the submitted protocol registration packet to ensure that all the required documents have been received. The ICFs **WILL NOT** be reviewed and approved by the DAIDS PRO and the site will receive an Amendment Registration Notification when the DAIDS PRO receives a complete registration packet. A copy of the Amendment Registration Notification should be retained in the site regulatory files.

For additional information on the protocol registration process and specific documents required for initial and amendment registrations, refer to the current version of the DAIDS Protocol Registration Manual.

12.3 COMPLIANCE WITH NIH GUIDELINES FOR RESEARCH INVOLVING PRODUCTS CONTAINING RECOMBINANT DNA

Because this study is evaluating products containing recombinant DNA, per NIH Guidelines for Research Involving Recombinant DNA Molecules, the study must be submitted to the site Institutional Biosafety Committee (IBC) and must be approved before participants are enrolled at

each respective institution. Investigators at each site are responsible for obtaining IBC approval and periodic review of the research per NIH guidelines section IV-B07-b-(6) and section IV-B-2-b. IBC review and approval must be documented by the investigator and submitted as part of protocol registration for this trial.

The NIH guidelines also require that the Recombinant DNA Advisory Committee (RAC) must submit human gene transfer trials conducted at or sponsored by institutions that receive NIH funds to the NIH Office of Biotechnology Activities (OBA) for review. The NIH guidelines create exceptions to RAC review for vaccines, which do not persist, and the RV460 Protocol team will submit a request for exemption with the study concept proposal for RAC review and response.

12.4 SPONSOR STUDY MONITORING

Kericho site visits by study monitors will be made per the IND sponsor's policy to monitor the following: study operations, the quality of data collected in the research records, the accuracy, and timeliness of data entered in the database, and to determine that all process and regulatory requirements are met.

Kericho site investigators will allow the study monitors, DAIDS, the KEMRI SERU, Kenya PPB, WRAIR IRB, USAMRDC, ORP, HRPO, other DoD regulatory agencies, and the FDA to inspect study documents (e.g., consent forms, drug distribution forms, case report forms), and pertinent hospital or clinic records for confirmation of the study data.

12.5 BIOHAZARD CONTAINMENT

As the transmission of HIV and other blood borne pathogens can occur through contact with contaminated needles, blood, and blood products, appropriate blood and secretion precautions will be employed by all personnel in the drawing of blood and shipping and handling of all specimens for this study, as currently recommended by the Centers for Disease Control and the National Institutes of Health. All dangerous goods materials, including diagnostic specimens and infectious substances, must be transported using packaging mandated by CFR 42 Part 72.

The International Air Transport Association Dangerous Goods Regulations for UN 3373, Biological Substance, Category B and Packing Instruction 650 will send all infectious specimens using packaging that meets requirements specified. Refer to individual carrier guidelines (e.g., Federal Express or Airborne) for specific instructions.

12.6 EXPECTED APPLICATION OF RESULTS

On completion, the study findings will be shared with all authorities having oversight of this protocol including the KEMRI SERU, Kenya PPB, WRAIR IRB, and Kenya's Ministry of Health. Results obtained from this study may inform considerations for the development of an HIV vaccine for use in the prevention of HIV infection and to fulfill a US FDA application.

The description of this study and the summary of results will be available on <http://www.ClinicalTrials.gov>.

Any new information from this study or other studies that may affect the participant's health, welfare, or willingness to continue with the study will be given to the participant by the appropriate method of contact, i.e., the participant will be contacted as soon as possible if, likely by phone in the case of a significant lab abnormality. The results of the study will be shared with the participants through a WRAIR IRB approved letter, at the participant's written request.

12.7 USE OF INFORMATION AND PUBLICATION

It is understood by the investigator that the information generated in this study may be used in connection with the development of the product and therefore may be disclosed to government agencies in various countries. To allow for the use of information derived from the study, the investigator is obliged to provide the sponsor with complete test results, all study data, and access to all study records. Confidentiality of participants will be maintained by exclusion of personally identifiable information from the research database and from any publications that result.

WRAIR recognizes the importance of communicating medical study data and therefore encourages their publication in reputable scientific journals and at seminars or conferences. Any results of medical investigations and or publication/lecture/manuscripts based thereon shall be exchanged and discussed by the investigator, and the USAMRDC and sponsor prior to submission for publication or presentation. Details of timelines are provided in Clinical Trial Agreements.

Results from investigations shall not be made available to any third party by the investigating team outside the publication procedure as outlined previously. WRAIR will not quote from publications by investigators in its scientific information and or promotional material without full acknowledgment of the source (i.e., author and reference). All publications written by WRAIR investigators must be reviewed and approved by the WRAIR Office of Research Technology and Applications (ORTA).

12.8 VOLUNTEER REGISTRY DATA SHEET

The USAMRDC requires that investigators complete data sheets on all participants participating in this protocol for entry into the Command's Volunteer Registry Database. This Volunteer Registry Database Sheet (VRDS) contains items of personal information, such as participant name, address, national identification number, study identity, and dates of participation.

The intent of this database is twofold: first, to readily answer questions about an individual's participation in research sponsored by the USAMRDC; and second, to ensure that USAMRDC can exercise its obligation to ensure that all research study participants are adequately warned (duty to warn) of risks and to provide new information as it becomes available. This information will be stored at USAMRDC for a minimum of 75 years and is kept confidential. The Volunteer Registry Data Sheet is a separate form and is not linked to the study database.

15 KERICHO BUDGET AND TIMEFRAME

15.1 KERICHO BUDGET

Item	Total Cost (USD)
1 Personnel	113,645
2 Equipment	56,976
3 Supplies (test kits, clinic and lab supplies, office consumables, and other study related supplies)	431,607
4 Travel (Domestic and Foreign)	83,116
5 Travel Training (Domestic and Foreign)	14,500
6 Other Expenses	193,004
7 Overheads (HJF MRI)	68,481
8 Overheads (HJF)	9,613
9 Other overheads	78,095
TOTAL BUDGET	1,049,037

15.1.1 KERICHO BUDGET JUSTIFICATION

15.1.1.1 Personnel

The amount allocated will provide salary support (and benefits to hired employees) to the Deputy Director of KEMRI and clinical research site leader in Kericho, and to the site PI and associate investigator, the Laboratory Director, Study Coordinator, Research Nurse, Pharmacist, Data Manager, Data QA/QC, Data entry specialist, a Regulatory staff and Finance Manager to assist with the study.

15.1.1.2 Equipment

The budget allocated for equipment is to purchase an ultra-low upright freezer and nitrogen tank to store patient samples in Year 3 of the study.

15.1.1.3 Supplies

The budget covers for laboratory, clinic and general supplies, to include test kits, reagents, quality control standards required by the protocol, specimen collection kits, tubes, pipets and pipet tips and other processing supplies. Office supplies include notebooks, pens, pencils, markers, labeling supplies and other materials for data collections and study execution including. General supplies cover operational expenses such as gasoline for travel, vehicle maintenance, fuel for backup generators, utilities and clinic security.

15.1.1.4 Travel

Travel expenses include Community Advisory Board member transportation expenses for meetings, volunteer recruitment, volunteer transportation and retention, hotel and per diem for staff responsible for transportation and tracking (in case required) and PI, co-PI and associate

investigators travel to local conferences to present study data and meeting in the US with the study PI and other MHRP collaborators.

15.1.1.5 Other expenses

[figure not shown]
This will cover expenses related to adverse event follow- up (in case needed) including referral to medical specialist (consultation and treatment), radiographic images or medications. It also includes expenses for compensation of study participants for study visits and optional procedures.

15.1.1.6 Overheads

Overhead includes those for HJF MRI and HJF.

15.2 TIME FRAME AND DURATION AT KERICHO

Table 7: Time Frame and Duration at Kericho

16 APPENDICES

APPENDIX A. SCHEDULE OF EVALUATIONS

Visit Number	S1	1	2	3	4	5	6	7	8	9	10	11	12	13	14	15	16	17	18	19	20	21	22	23	24	25	26 Exit	
Visit Day	-45 to -3	0	3 ± 1	7 ± 2	14 ± 3	28 ± 7	35 ± 2	42 ± 3	84 ± 7	87 ± 1	91 ± 2	98 ± 3	140 ± 7	143 ± 1	147 ± 2	154 ± 3	224 ± 7	231 ± 2	238 ± 3	392 ± 7	395 ± 1	399 ± 2	406 ± 3	476 ± 14	560 ± 14	728 ± 14	735 ± 14	
Visit week		0	0.5	1	2	4	5	6	12	12.5	13	14	20	20.5	21	22	32	33	34	56	56.5	57	58	68	80	104	105	
Clinical																												
Briefing & contact information	X																											
Informed consents	X																											
Test of understanding	X																											
Complete physical exam, height, weight & review medical history	X																											
Vital signs (BP, pulse, RR, oral temp)	X	X	X	X	X	X	X	X	X	X	X	X	X	X	X	X	X	X	X	X	X	X	X	X	X	X		
Concomitant Medication	X	X	X	X	X	X	X	X	X	X	X	X	X	X	X	X	X	X	X	X	X	X	X	X	X	X		
Targeted physical exam and review of symptoms	X	X	X	X	X	X	X	X	X	X	X	X	X	X	X	X	X	X	X	X	X	X	X	X	X	X		
HIV risk counseling; pregnancy counseling ¹¹	X	X	X	X	X	X	X	X	X	X	X	X	X	X	X	X	X	X	X	X	X	X	X	X	X	X		
Vaccination¹³	X ⁶			X ⁶		X ⁶		X ⁶		X ⁶		X ⁶		X ⁶		X ⁶		X ⁶		X ⁶		X ⁶		X ⁶		X ⁶		
Review Eligibility	X			X			X			X			X			X		X		X		X		X		X		
Enrollment and randomization ¹²	X																											
Assess reactogenicity in clinic 30-60 min post-vaccination	X			X			X			X			X			X		X		X		X		X		X		
MAAE documentation ⁹	X	X	X	X	X	X	X	X	X	X	X	X	X	X	X	X	X	X	X	X	X	X	X	X	X	X		
Adverse Event documentation	X	X	X	X	X	X	X	X	X	X	X	X	X	X	X	X	X	X	X	X	X	X	X	X	X	X		
Diary card completion/review ¹⁰		X	X		X		X		X	X		X	X		X	X		X		X	X		X	X				
Clinical Laboratory Assessments⁵																												
Urinalysis dipstick for blood, protein and glucose	X																											
Urine-pregnancy test ⁷	X	X			X		X	X		X ²	X		X	X		X	X		X ²	X	X	X		X	X	X		
CBC with differential	3		3			3			3			3			3			3			3			3				
Creatinine, ALT, AST	3		3			3			3			3			3			3			3			3				
Syphilis serology	6																											
HBsAg/HepC	NB																											
Pap smear for Softcup collection participants	X																											
Coagulation and safety tests prior lymph node biopsy ⁸																												
HIV testing with Pre/Post HIV test counseling	6	6																								6	6	
Research Laboratory Assessments³																												
HIV NAb		6		6	6	6	6	6	6	6	6	6	6	6	6	6	6	6	6	6	6	6	6	6	6	6	6	
Binding antibody/antibody profiling		6		6	6	6	6	6	6	6	6	6	6	6	6	6	6	6	6	6	6	6	6	6	6	6	6	
Functional Antibody Assays (ADCC, ADCP, ADCVI, etc)		NB		NB	NB	NB	NB	NB	NB	NB	NB	NB	NB	NB	NB	NB	NB	NB	NB									
Cellular immune analysis		93.5	17	17	42.5		25.5	42.5		17	34	85		17	34	68		34	68		17	34	85	85	85	85	34	
Cytokine/soluble factor assays		NB		NB	NB	NB	NB	NB	NB	NB	NB	NB	NB	NB	NB	NB	NB	NB										
Gene expression/transcriptome analysis		34	17							17	17		8.5	17	17						17	17		8.5				
Mucosal secretion collection ^{1,7}		X								X			X		X			X			X	X	X	X	X			
Lymph node biopsy ²													X									X						
Storage & additional immunogenicity testing (mL)		25.5			17	17				8.5			17	8.5				34	17			17	51	25.5	25.5	25.5	17	

Visit Number	S1	1	2	3	4	5	6	7	8	9	10	11	12	13	14	15	16	17	18	19	20	21	22	23	24	25	26 Exit
Visit Day	-45 to -3	0	3 ± 1	7 ± 2	14 ± 3	28 ± 7	35 ± 2	42 ± 3	84 ± 7	87 ± 1	91 ± 2	98 ± 3	140 ± 7	143 ± 1	147 ± 2	154 ± 3	224 ± 7	231 ± 2	238 ± 3	392 ± 7	395 ± 1	399 ± 2	406 ± 3	476 ± 14	560 ± 14	728 ± 14	735 ± 14
Visit week		0	0.5	1	2	4	5	6	12	12.5	13	14	20	20.5	21	22	32	33	34	56	56.5	57	58	68	80	104	105
Daily volume (mL) ^{4,5}	18	171	34	23	77.5	29	31.5	60.5	37.5	34	49	134.5	37.5	34	40	126	29	40	126	46	34	66	168.5	122.5	128.5	128.5	63
Cumulative volume (mL) ^{4,5}	18	189	223	246	323.5	352.5	384	444.5	482	516	565	699.5	737	771	811	937	966	1006	1132	1178	1212	1278	1446.5	1569	1697.5	1826	1889
8 week cumulative volume ^{4,5}								444.5	158.5	163.5	212.5	315.5	292.5	289	295	372	29	69	195	46	80	146	314.5	122.5	128.5	128.5	191.5

NB=No extra blood required

1: Mucosal secretion collections - Rectal secretions collected by sponge.-Male participants: semen collection by masturbation. Female participants: cervicovaginal secretions collected by Softcup.
for menstruating females, mucosal collection window can be extended to -3 + 14 days.

2: Excisional inguinal lymph node biopsies will be performed in a subset of participants who agree to undergo this procedure. Urine pregnancy testing prior to procedure. Biopsy site assessment at 7 days (+2 days) after each biopsy.

3: Research labs may be performed at any visit where sufficient stored samples are available.

4: The maximum amount drawn in any 8 week interval is 444.5 mL. The maximum amount drawn in one day is 171 mL.

5: Clinical labs may be repeated if clinically significant.

6: Phone or clinic visit will be done to assess the participants well-being 24 hours (+1 day) after each vaccination.

7: Pregnancy testing must be performed prior to vaccination and mucosal secretion collection

8: 9ml should be taken if CBC/Chem results not available on day of biopsy. Otherwise, 3ml should be drawn

9: Medically Attended Adverse Events will be followed through the end of the study, a full 12 months following the last vaccination

10: Participants will take home the diary card and complete and the diary card will be reviewed at 7 days after vaccination.

11: Additional testing as clinically indicated

12: A participant is considered enrolled into the study once they are randomized into a study group

13: Study vaccination outside of a participant's vaccination window may occur at the discretion of the PSRT.

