5.5 STUDY VISITS

Participants will have up to 26 clinic visits. The active study phase will last a total of 105 weeks, which will include the time of the first screening visit through the final clinic study visit. In addition, participants will be contacted once per week for 3 weeks (3 phone contacts) following the 105 week active study phase. At these contacts, staff will collect the information listed below.

- Confirmation of vital status; if deceased, attempt to learn cause and date of death;
- If participant is alive, record the participant's responses to questions regarding any occurrence of the following events since the last study contact:
 - Life-threatening adverse experiences;
 - Persistent or significant disability/incapacity;
 - Hospitalizations and reasons;
 - New diagnosis of HIV infection; and
 - Pregnancies and outcomes, including congenital anomalies/birth defects

All such events will be recorded, and adverse events other than HIV infection will be assessed for relationship to study product(s). Clinic visits will only be required if HIV confirmatory testing is necessary; however, a clinic visit may be arranged for other reasons.

Evaluation of the safety of the study vaccines is outlined in the schedule of evaluations (SOE) and will include laboratory studies, medical history, physical assessment by clinicians, and participant self-assessment recorded on a 7-day diary card. Additional study visits may be required if, in the investigator's opinion, any lab value warrants repeating. The first vaccination visit could take up to 6 hours, but the other vaccination visits take about 4 hours each. Most other follow-up clinic visits will usually take about 2 hours.

Total blood volume drawn from each participant will not exceed the US Department of Defense (DoD), American Association of Blood Banks (AABB) and FDA guidelines of 450 mL in an eight-week period. If a participant is anemic, each visit's blood volume will be reviewed, and the blood drawn for research may be reduced or not drawn at all, depending on the severity of anemia.

Table 4: Visit Procedures

Clinic visit activities

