6.1.1.1 Laboratory tests to assess safety

Clinical laboratory testing will take place in the CAP-certified laboratory and includes pregnancy testing, complete blood count, chemistry (Creatinine, ALT, AST) and HIV testing. HIV testing will be performed according to the approved laboratory algorithm including 4th generation immunoassay and nucleic acid testing when indicated. Safety labs may be repeated if clinically indicated.

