Follow-up on participant well-being will be performed by telephone (preferred method) or clinic visit on the day following vaccination (and up to 48 hrs. later). Diary cards will be reviewed with the clinician on day 7 ± 2 following each vaccination. If upon reviewing the diary card, the clinician finds that local or systemic information (except swelling, redness, temperature measurements) is missing from the diary card, or the diary card is lost, the participant will be asked to provide the missing information to the best of their recollection. The missing data, such as temperature measurements will be indicated as missing in the database and a lost diary card will not result in a protocol deviation.

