10.2.2 REPORTING AND MANAGEMENT OF PARTICIPANTS WHO BECOME PREGNANT

Pregnant women are excluded from enrollment, however, if a participant becomes pregnant during the study, further vaccinations will be stopped, and she will be referred for maternal and child health services. Participants will continue to be followed for the remainder of the study period for safety, and the study team will follow the course of the pregnancy until the outcome is documented. During subsequent study visits, blood draws (6 mLs for basic chemistry and hematology) will be conducted for safety evaluations only. No optional collections or procedures will be performed.

The PI or designated associate investigator will be responsible for reporting any pregnancy to the PSRT and the study database. The PSRT will review this information. The site PI will forward notification as necessary to the WRAIR IRB and KEMRI SERU.

Pregnancy outcomes will be recorded via a standardized case report form. Information documented on this form will include the date of last menstrual period, the date that the pregnancy was confirmed, any history of complications during prior pregnancies (such as congenital abnormalities or spontaneous abortions), and the outcome of the pregnancy including date of termination or delivery, any complications of pregnancy, and the status of the child. A separate case report form will be completed for the delivered child to document date of delivery, gender, weight, the presence of any congenital abnormalities, American Pediatric Gross Assessment Record (APGAR) score, HIV status, and any other complication of delivery.

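### Appendix A's stated 8-week maximum of 444.5 mL is a nominal-day, no-repeat total: one permitted repeat safety panel takes it past the 450 mL limit, and the unstated anchor for post-dose visit windows leaves a larger excess possible

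*Protocol*

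**What the plan says.** Section 5.5 commits that the blood drawn from each participant will stay within "FDA guidelines of 450 mL in an eight-week period". Appendix A, footnote 4, gives the planned maximum: "The maximum amount drawn in any 8 week interval is 444.5 mL".

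The daily volumes in Appendix A are, in mL, "18 171 34 23 77.5 29 31.5 60.5" for screening to visit 7 and "37.5 34 49 134.5 37.5 34 40 126" for visits 8 to 15. The same table gives dose 3 (visit 8) on day 84 ± 7, dose 4 (visit 12) on day 140 ± 7, visit 9 on day 87 ± 1, visit 10 on day 91 ± 2 and visit 15 on day 154 ± 3. Screening may fall from day -45 to day -3.

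Three other statements bear on the total:
- Repeat tests are allowed. Footnote 5 says "Clinical labs may be repeated if clinically significant", and section 6.1.1.1 says "Safety labs may be repeated if clinically indicated".
- The volume of one safety panel appears in section 10.2.2: "blood draws (6 mLs for basic chemistry and hematology". This agrees with the 3 mL each for CBC and chemistry in Appendix A.
- Section 8.1.1.1 counts the one-week review from the dose: "Diary cards will be reviewed with the clinician on day 7 ± 2 following each vaccination". Footnote 10 of Appendix A also places that review 7 days after vaccination.

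**The concern.** Footnote 4 is worded as a bound on every 8-week interval, yet it takes no account of the visit windows or the repeat tests that the same appendix allows. The 450 mL limit is the protocol's own participant-safety ceiling. The visible control on it is the printed row of 8-week totals, and section 5.5 describes a review of each visit's volume only for an anemic participant. If the printed maximum can be exceeded within the allowed conduct of the trial, a site that relies on the table gets no warning. The draw most exposed is visit 15, which takes 126 mL and is shown with an 8-week total of only 372 mL.

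**Working it through.** **Reproducing the plan's figure.** Place each visit on its nominal day, with screening on day -3, and add the daily volumes of all visits at most 56 days apart.
- Screening to visit 7: 18 + 171 + 34 + 23 + 77.5 + 29 + 31.5 + 60.5 = 444.5 mL, as printed.
- Ending at visit 15 (day 154): the window reaches back to visit 11 (day 98), so 134.5 + 37.5 + 34 + 40 + 126 = 372 mL, as printed.

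Every other printed entry in the row is reproduced in the same way. The row therefore counts both ends of a 56-day span, uses nominal days and includes no repeats.

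**Repeat tests.**
- Room under the limit: 450 - 444.5 = 5.5 mL.
- One CBC plus chemistry: 3 + 3 = 6 mL.
- Total: 444.5 + 6 = 450.5 mL, which is 0.5 mL over.
- Condition: screening and visit 7 must be at most 56 days apart. With visit 7 on day 42, screening is on or after day -14 (42 + 14 = 56). With visit 7 at its earliest, day 39, screening is on or after day -17 (39 + 17 = 56).
- With earlier screening, visits 1 to 7 total 444.5 - 18 = 426.5 mL, and a repeat gives 432.5 mL, within the limit.

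**Visits 8 to 15, windows counted from day 0.** The latest visit 8 is day 91 and the earliest visit 15 is day 151. They are at least 151 - 91 = 60 days apart and never share an 8-week interval. The most that can end at visit 15 remains 372 mL.

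**Can that reading be applied?** Suppose dose 3 is given on day 91, which is in window.
- Visit 9, the 3-day post-dose visit, has a printed window of days 86 to 88, before the dose.
- The section 8.1.1.1 review falls on days 96 to 100 (91 + 7 ± 2). Visit 10, the one-week visit, has a printed window of days 89 to 93. The two do not overlap.

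**Visits 8 to 15, windows counted from the dose.**
- Shortest gap from dose 3 to dose 4: 133 - 91 = 42 days.
- Visit 15 is 14 ± 3 days after dose 4. Visits 8 to 15 span gap + 14 days, or gap + 11 with visit 15 at its earliest. The span is at most 56 days when the gap is at most 42 or 45 days respectively.
- Total: 37.5 + 34 + 49 + 134.5 + 37.5 + 34 + 40 + 126 = 492.5 mL, which is 42.5 mL (42.5/450 = 9.4%) above the limit and 48 mL above footnote 4.

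**Pre-biopsy blood.** Visit 10 is 49 mL, against 40 mL at visits 14 and 17. The 9 mL difference matches the larger pre-biopsy volume in footnote 8. This is an inference, because the cells of that row are empty in the text available. Lymph node biopsy is optional. Without the 9 mL:
- Visits 8 to 15: 492.5 - 9 = 483.5 mL, still 33.5 mL over.
- Visits 9 to 15: 455 - 9 = 446 mL, or 449 mL with the smaller 3 mL volume of footnote 8. Both are under 450 mL, so visits 9 to 15 alone exceed the limit only with the full 9 mL.

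**The case against.** The best defence is that section 5.5 sets the binding rule. Volume is not to exceed 450 mL whatever a footnote adds up to, so a breach would be a departure from the protocol and not something it schedules. That stands. It means that the table fails to show when the rule is at risk, not that the rule is absent.

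A reader might infer that the printed windows themselves permit 492.5 mL. They do not: as printed study days, visits 8 and 15 cannot be closer than 60 days. The larger total needs post-dose visits to move with the dose. The protocol says so for the one-week review but not for the two-week visit that carries the 126 mL. It also needs dose 3 late and dose 4 early by a combined 11 to 14 days, and the full 492.5 mL appears to apply only to participants having a biopsy.

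The repeat-panel excess is 0.5 mL. It requires both tests to be repeated (one alone gives 447.5 mL) and screening close to day 0. The volume rows also carry a reference to footnote 5, so readers are told that repeats may occur. These points limit the size. They do not rescue the word maximum, because even a single 3 mL repeat exceeds 444.5 mL. Nothing in the protocol shows that staff would ignore the limit or hold back a repeat safety test, and the point does not depend on either.

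**Conclusion.** Footnote 4 is wrong as a statement about any 8-week interval. It is a nominal-day, no-repeat total.
- Without any assumption about window anchors, one permitted CBC plus chemistry repeat gives 450.5 mL when screening is within about 14 days before day 0 (17 days if visit 7 is at its earliest).
- If post-dose visits follow the actual dose, a dose 3 to dose 4 gap of 42 to 45 days gives 492.5 mL within 56 days, or about 483.5 mL without the inferred pre-biopsy blood.

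The second result is conditional. The protocol does not state the anchor, although section 8.1.1.1, footnote 10 and the impossibility of visit 9 preceding its dose make counting from the dose the workable reading. The nominal schedule stays within 450 mL, and the documents do not support saying that the trial plans a breach. The correction is still worth making, because the wrong figure concerns a safety ceiling that the protocol sets for itself.

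**What to change.** Make three changes to Appendix A:
- State that post-dose visit windows count from the actual dose, so that the table agrees with section 8.1.1.1 and footnote 10.
- Relabel 444.5 mL in footnote 4 as the nominal-day total without repeats, and add the worst case over the allowed windows: 492.5 mL before repeats, with the pre-biopsy volume shown separately.
- Require a rolling 56-day total before each draw. Where it would pass 450 mL, counting any repeat safety panel, reduce storage tubes and other research tubes at that visit, not safety tubes. A rolling total also covers doses given outside their windows under footnote 13, which no fixed table can.

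The administrative cost is a footnote and a running total in the source form or database. The scientific cost is research blood around visit 15 in participants with a short dose 3 to dose 4 gap: at most 492.5 - 450 = 42.5 mL, or 48.5 mL with one repeat panel. A few mL of storage blood may also be lost by visit 7.
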